9.4. Vital Signs

Descriptive summaries of actual values and changes from baseline (last value observed prior to the first dose of study drug) will be calculated by treatment group (treatment cohort for Part 2) for systolic blood pressure, diastolic blood pressure, heart rate, respiratory rate, and oral body temperature at each post-baseline timepoint.

In addition, potentially clinically significant results of vital signs identified using prospectively defined criteria (Table 4) will also be summarized descriptively.

Table 4: Potentially Clinically Important Criteria (PCS): Vital Signs

Heart Rate Decrease of ≥ 20 beats/min or ≤ 40 beats/min
Heart Rate Increase of ≥ 20 beats/min or ≥ 120 beats/min
Diastolic Blood Pressure Decrease of \geq 20 mmHg or \leq 50 mmHg
Diastolic Blood Pressure Increase of \geq 20 mmHg or \geq 105 mmHg
Systolic Blood Pressure Decrease of \geq 25 mmHg or \leq 90 mmHg
Systolic Blood Pressure Increase of $\ge 25 \text{ mmHg or} \ge 180 \text{ mmHg}$
Weight Decrease of $\geq 10\%$
Weight Increase of $\geq 10\%$

Individual data listings of vital sign results will be presented for each participant. Values that meet vital sign PCS will be flagged in the listings (see Table 4).

9.5. Electrocardiograms

For Part 1 and Part 2, observed values and changes from baseline (last value observed prior to the first dose of study drug) at each post-baseline timepoint for continuous ECG parameters including heart rate, ventricular rate, PR interval, QRS duration, QT interval (uncorrected), and QTcF interval will be summarized by treatment group (treatment cohort for Part 2) using descriptive statistics (n, mean, SD, median, minimum, and maximum).

Overall evaluation of ECG will be summarized using frequency counts and percentage of participants as normal or abnormal, and the relevance of the abnormality will be summarized by CS or NCS. QTcF will be summarized using frequency and percentage for the following categories:

Participants with the highest QTcF post-baseline value:

- < 450 msec
- 450-480 msec
- \geq 480 msec

Participants with the highest QTcF change value:

- < 30 msec
- 30-60 msec
- > 60 msec

Potentially clinically important criteria (Sponsor defined):

• \geq 450 msec

In addition, a summary shift table comparing baseline interpretation (normal, abnormal - NCS, abnormal - CS) to the Investigator interpretation at each time point will also be presented.

ECG results will be listed by treatment group (treatment cohort for Part 2) for all participants. Additionally, a listing will be provided for Investigator-identified ECG abnormalities.

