5.6 Diet, Fluid, and Activity Control

Restriction of excess dietary sodium and cooked meat protein may prove beneficial to participants with a history of, or predisposition for, hypertension or kidney disease in general. In the absence of alternate regional practices, dietary salt should be restricted to <5g/day and dietary cooked meat protein to <1 g/kg/day. In addition, the amount of meat protein should remain stable from day-to-day, and an increased consumption of meat should not occur the day before scheduled serum creatinine measurements.

Participants will refrain from consumption of grapefruit or Seville oranges (or their juices) from 7 days prior to the first dose of study drug until after the completion of the study.

Increased fluid intake is encouraged in participants with ADPKD. Given the potential for dehydration with lixivaptan treatment, all participants should be instructed to ingest fluids in anticipation of, or at the first sign of, thirst in order to avoid excessive thirst or dehydration. At the initiation of the Placebo Run-In Period, all participants should receive the recommendation to ingest at least 3-4 quarts (or liters as an approximation of quarts) of fluid (including in solid, semi-solid, and liquid foods) per day, unless otherwise directed by the

Investigator. This recommendation should start at the beginning of the Placebo Run-In Period and continue through the end of the study (Part 1 and Part 2). Additionally, participants should ingest 1 to 2 cups (approximately 250-500 mL) of water before bedtime regardless of perceived thirst and replenish fluids overnight with each episode of nocturia. Dehydration can be monitored by participant self-assessment of symptoms such as lightheadedness or dizziness.

Daily activity including exercise should remain stable during the study and participants should avoid heavy lifting or intense physical exertion on the day before scheduled serum creatinine measurements.

Consumption of alcohol should be limited to 1 alcoholic drink equivalent per day in women and 2 alcoholic drink equivalents per day in men. An alcoholic drink equivalent is 12 ounces (360 ml) of regular beer, or 5 ounces (150 ml) of wine, or 1.5 ounces (45 ml) of distilled spirits.

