8.13.4 ECGs

For Part 1, observed values and changes from baseline (last value observed prior to the first dose of study drug) at each post-baseline timepoint for continuous ECG parameters including heart rate, ventricular rate, PR interval, QRS duration, QT interval (uncorrected), and QTcF interval will be summarized by treatment group using descriptive statistics (n, mean, SD, median, minimum, and maximum).

A summary shift table comparing the baseline (last value observed prior to the first dose of study drug) interpretation (normal, abnormal - NCS, abnormal - CS) to the Investigator interpretation at each post-baseline time point will also be presented by treatment group.

A listing will be provided for Investigator-identified ECG abnormalities from safety ECGs. The overall evaluation of safety ECGs will be summarized by treatment group using frequency counts and percentage of participants as normal or abnormal, and the relevance of the abnormality will be summarized as CS or NCS.

For Part 2, observed values and changes from baseline (last value observed during Follow-up Period I in Part 1) at each post-baseline assessment timepoint for continuous ECG parameters including heart rate, ventricular rate, PR interval, QRS duration, QT interval (uncorrected), and QTcF interval will be summarized for all participants using descriptive statistics (n, mean, SD, median, minimum, and maximum).

A summary shift table comparing the baseline (last value observed during Follow-up Period I in Part 1) interpretation (normal, abnormal - NCS, abnormal - CS) to the Investigator interpretation at each post-baseline time point will be presented for all participants.

A listing will be provided for Investigator-identified ECG abnormalities from safety ECGs. The overall evaluation of safety ECGs will be summarized for all participants using frequency counts and percentage of participants as normal or abnormal, and the relevance of the abnormality will be summarized as CS or NCS.

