8.13.6 Vital Signs

For Part 1, changes from baseline (last value observed prior to the first dose of study drug) in vital signs at each post-baseline timepoint will be summarized by treatment group using descriptive statistics (n, mean, SD, median, minimum, and maximum).

For Part 2, changes from baseline (last value observed during Follow-up Period I in Part 1) in vital signs at each post-baseline timepoint will be summarized for all participants using descriptive statistics (n, mean, SD, median, minimum, and maximum).

For Part 1 and Part 2, the change from baseline is defined as the post-baseline value minus the baseline value. There will not be any imputation for missing values. All vital sign data will be listed individually by each participant based on the respective analysis population.

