4.2.3.1. Exploratory Endpoints

- The annualized percent change in htLV determined by MRI from baseline (posttreatment follow-up visit [Visit 25] after Week 52 in Part 1) to post-treatment follow-up during Follow-up Period II after Week 104 for on-treatment completers, or, for participants who discontinue study drug treatment prior to Week 104 [Visit 42], during the Follow-up Period 28 days following study drug treatment discontinuation in Part 2;
- Mean change from baseline in morning spot urine osmolality in Part 2; Baseline is defined as urine osmolality obtained at 28 days post-treatment follow-up visit (Visit 25) after Week 52 in Part 1.
- The annualized change in eGFR calculated from the 2021 CKD-EPIcr-cys_R equation from baseline to the post-treatment follow-up. The definitions of baseline eGFR, post-treatment follow-up eGFR and annualization are the same as the key comparison endpoint in Part 2 (Section 4.2.1.1) except for using the different eGFR equations.

5. Analysis Populations

The following analysis populations are planned for this study:

Part 1:

- **Placebo Run-in Safety Set:** The Placebo Run-in Safety Set includes all participants who received at least one dose of placebo during Placebo Run-In Period in Part 1.
- Lixivaptan Titration Safety Set: The Lixivaptan Titration Safety Set includes all participants who received at least one dose of lixivaptan during Lixivaptan Titration Period in Part 1.
- **Randomized Safety Set:** The Randomized Safety Set includes all participants who received at least one dose of study drug after randomization.
- Intent-to-Treat Analysis Set (ITT): The ITT includes all participants who were randomized in Part 1.

- **Modified Intent-to-Treat Analysis Set (mITT):** The mITT includes all participants in the ITT who received at least one dose of study drug in Part 1. Note that the mITT Analysis Set consists of the same set of the participants in the Randomized Safety Set.
- **Primary Efficacy Analysis Set (PEAS):** The PEAS includes all participants in the mITT Analysis Set who have both baseline and at least one assessment of eGFR after the treatment is complete or discontinued in Part 1.
- Secondary Efficacy Analysis Set (SEAS): The SEAS includes all participants in the mITT Analysis Set who have both baseline and at least one on-treatment assessment of eGFR.

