8.11.2. Urine Osmolality

Descriptive statistics for the change from baseline (Visit 2) in morning spot urine osmolality will be presented for the participants in the P2EAS by treatment cohort and overall at each scheduled time point. The number (%) of participants who show suppressed urine osmolality by treatment cohort and overall, defined by two levels of spot urine osmolality \leq 250 mOsm/kg and \leq 300 mOsm/kg will be summarized descriptively at each time point.

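### SAP 9.4, 9.5 and 8.11.2 give Part 2 vital signs, ECG and urine osmolality a pre-treatment baseline, contrary to the protocol (ECG, vital signs) or to SAP 4.2.3.1 (osmolality), and SAP 15 does not record it

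*SAP*

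**What the plan says.** **ECG.** SAP 9.5 applies one rule throughout: "For Part 1 and Part 2, observed values and changes from baseline (last value observed prior to the first dose of study drug"). Protocol 8.13.4 treats Part 2 separately: "For Part 2, observed values and changes from baseline (last value observed during Follow-up Period I in Part 1"). It repeats that baseline for the Part 2 shift table.

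**Vital signs.** SAP 9.4 also has one rule, "changes from baseline (last value observed prior to the first dose of study drug) will be calculated by treatment group", and a bracket straight after it extends the rule to the Part 2 cohorts. Protocol 8.13.6 says "For Part 2, changes from baseline (last value observed during Follow-up Period I in Part 1").

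**Urine osmolality.** Here the SAP disagrees with itself. The Part 2 endpoint in SAP 4.2.3.1 reads "Baseline is defined as urine osmolality obtained at 28 days post-treatment follow-up visit (Visit 25) after Week 52 in Part 1". The Part 2 analysis in SAP 8.11.2 reads "Descriptive statistics for the change from baseline (Visit 2) in morning spot urine osmolality". Protocol 2.2.2.7 and 8.10.2 name no Part 2 baseline visit, so the protocol does not settle the matter.

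**Change log.** SAP 15 undertakes to document departures from the protocol. It lists the analysis populations, the move to height-adjusted liver volume, percent change, the added lixivaptan safety summaries and the removal of the blinded sample size re-estimation. It lists no change of Part 2 baseline.

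**The concern.** A Part 2 safety table should show what happened in Part 2. If its changes are taken from a value recorded before any study drug, each figure combines whatever remained from Part 1 with whatever arose in Part 2, and the table does not separate them. In the cohort that took placebo in Part 1, the Part 2 change would also span a year off lixivaptan.

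The SAP's Part 2 tables would then rest on two different baselines without saying so. For osmolality a programmer cannot follow both SAP sections. A Visit 2 baseline also precedes the advice to drink more, of which protocol 5.6 says: "This recommendation should start at the beginning of the Placebo Run-In Period and continue through the end of the study". A change from Visit 2 would therefore include any effect of that advice.

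**Working it through.** No figure in the plan needs reproducing. The check compares the texts, adds up the planned schedule and uses one identity.

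**1. Which dose is meant.** SAP 4.1.4.2 identifies the first dose of study drug as the run-in placebo. SAP 9.7 uses the same phrase for Part 1 only and contrasts it with Follow-up Period I for Part 2. The phrase in SAP 9.4 and 9.5 therefore cannot reasonably mean the first Part 2 dose.

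**2. Part 2 baselines side by side.**

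| Variable | SAP Part 2 baseline | Comparison text |
|---|---|---|
| ECG | Before first study drug dose (9.5) | Follow-up Period I (protocol 8.13.4) |
| Vital signs | Before first study drug dose (9.4) | Follow-up Period I (protocol 8.13.6) |
| Urine osmolality | Visit 2 (8.11.2) | Visit 25 (SAP 4.2.3.1) |
| eGFR | Follow-up Period I (4.2.1.1, 8.7) | Agrees with protocol 8.6.1 |
| htTKV | Visit 25 (8.9.2) | Agrees with protocol 8.7.2 |
| Patient-reported outcomes | Visit 25 (4.2.2.4, 8.10) | Left to the SAP by protocol 8.9.2 |
| Laboratory | Follow-up Period I (9.3) | Agrees with protocol 8.13.3 |
| Weight and BMI | Follow-up Period I (9.7) | BMI agrees with protocol 8.13.5 |

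The first three rows are out of line with the rest.

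**3. Time between the two baselines** (protocol Table 3, visit windows ignored). The last vital signs and the osmolality specimen before the first dose fall at Visit 2. Run-in 1 + titration 5 to 6 + double-blind 52 + follow-up 4 = 62 to 63 weeks to Visit 25. The only ECG before the first dose is at Visit 1a. Adding screening gives 3 + 62 = 65 to 8 + 63 = 71 weeks, which matches the synopsis duration for Part 1.

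**4. What enters the Part 2 figure.** Let a be the net change from the pre-treatment value to Follow-up Period I, and b the change from there to the Part 2 value.

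- Change under the SAP rule = a + b
- Change under the protocol rule (SAP 4.2.3.1 for osmolality) = b

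The two differ by a, which is the Part 1 change still present at the Follow-up Period I measurement.

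Take the heart-rate criterion in SAP Table 4, an increase of at least 20 beats/min. As an illustration, let each component be half the threshold: a = 10 and b = 10. Then a + b = 20, which is flagged under the SAP rule, while b = 10 is not flagged under the protocol rule. Conversely, with a = -10 and b = 20, a + b = 10 and the SAP rule misses a change that the protocol rule flags.

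The same reasoning applies to the blood-pressure change limbs (20 mmHg diastolic, 25 mmHg systolic) and to the QTcF change bands (<30, 30-60, >60 msec). The ECG shift table starts from the wrong category in the same way.

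**5. What does not depend on baseline.** The absolute limbs of Table 4, QTcF >=450 msec and the osmolality counts at <=250 and <=300 mOsm/kg are unchanged.

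**6. Availability.** Protocol 6.5.2 schedules ECG, vital signs, weight and urine osmolality at Visit 25, so the Follow-up Period I baseline needs no new data.

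**The case against.** The best defence is that a pre-treatment baseline is not wrong in itself. In participants on lixivaptan in both parts, Visit 25 follows a year of drug, and a Follow-up Period I baseline removes any persisting cumulative effect from the Part 2 tables. Protocol 8.14 lets the SAP modify the plan and asks for an amendment only for major changes to the primary analysis. This stands as a reason to show a cumulative summary. It does not explain why SAP 15 is silent, why laboratory data and weight use the other baseline, or how SAP 8.11.2 and 4.2.3.1 can both be followed.

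A reader might also infer more than the documents support:

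- **That all Part 1 change is reported as Part 2 change.** Only net change still present at Follow-up Period I, at Visit 25 about 28 days off drug, carries over. Change that has reversed by then does not.
- **That weight has two Part 2 baselines.** One could reason that a 6% loss in Part 1 and a 5% loss in Part 2 give 1 - 0.94 x 0.95 = 10.7%, and so trip the 10% criterion in Table 4. But the baseline sentence in SAP 9.4 does not list weight, Table 4 names no baseline, and the only stated Part 2 weight baseline is Follow-up Period I (SAP 9.7). This is a gap, not a conflict.
- **That the QTcF clinical-importance criterion shifts.** It is an absolute value. Only the descriptive change bands move.
- **That a Visit 25 osmolality baseline isolates the drug effect.** Part 2 is single-arm and open-label, so neither baseline gives a controlled estimate.
- **That about 1215 participants are affected.** That is the planned Part 2 number. SAP 12 reports 5 randomized, all stopped in Part 1, and no statistical analyses.

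**Conclusion.** The point holds as a minor consistency correction. SAP 9.4 and 9.5 depart from the protocol on the Part 2 baseline, SAP 8.11.2 contradicts SAP 4.2.3.1, and none of it is logged. What is exposed is the descriptive Part 2 change summaries for these three variables, the change limbs of the heart-rate and blood-pressure criteria, the QTcF change bands and the ECG shift table. No primary, secondary or key liver-safety analysis is touched.

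The size of the distortion for any participant is the net change remaining at Follow-up Period I. The documents give no figure for that, so none is claimed. The conclusion assumes that the first dose of study drug means the run-in placebo, as SAP 4.1.4.2 states. No Part 2 result is affected, since no participant reached Part 2.

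**What to change.** - **SAP 9.4:** state that the Part 2 baseline is the last Follow-up Period I value. Apply it to the change criteria in Table 4, and name the weight baseline there in line with SAP 9.7.
- **SAP 9.5:** state the same Part 2 baseline, including for the QTcF change bands and the shift table.
- **SAP 8.11.2:** replace Visit 2 with Visit 25, to agree with SAP 4.2.3.1.
- **If cumulative change from the pre-treatment value is also wanted:** present it as a separately labelled summary and record it in SAP 15.

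The cost is three short wording edits and one baseline flag in programming. No new data are needed.

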9.6. Lixivaptan Treatment Safety Analysis

The lixivaptan treatment safety will summarize the following safety information occurred post the first dose of lixivaptan treatment after randomization during the study based on the LTSS by treatment cohort and overall:

- Incidence of special liver events (ALT > 3 x, AST > 3 x, ALT or AST > 3 x, and Total Bilirubin > 2 x ULN)
- Kaplan-Meier product-limit curve for special liver events
- Summaries of TEAEs (see Section 9.2)

- Overall summary of TEAEs
- o TEAEs by preferred term and causality
- TEAEs by preferred term and severity
- Treatment-related TEAEs by preferred term and severity

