Double-blind, Randomized Treatment Period (Visits 10 to 22): Following successful completion of titration, participants will be randomized 2:1 (lixivaptan: placebo) to continue to receive lixivaptan at the dose achieved at the end of the Lixivaptan Titration Period or to matching placebo in a double-blind fashion for 52 weeks. Study visits will be scheduled every 4 weeks during this period. Assessments at each visit are detailed in the [Schedule of Procedures – Part 1](#).

Follow-up Period I (Visits 23 to 25): Three visits will occur over a 28-day, study drug-free period following the last dose of study drug. Blood samples will be drawn at 3 time points for serum creatinine and serum cystatin C, to determine eGFR for primary and exploratory analyses, respectively. The first visit (Visit 23) will occur on the 8th day (+ 3 days) after the last dose of study drug, and the last visit (Visit 25) will occur on the 28th day (\pm 3 days) after the last dose of study drug. Visit 24 must be scheduled to occur at least 24 hours after Visit 23 and at least 24 hours prior to Visit 25. At Visit 25, additional efficacy and safety assessments will be performed; a post-baseline MRI for assessment of TKV and LV is to be obtained between 25 days and 31 days post last dose of study drug and must be completed prior to or on the same day as all other Visit 25 study procedures. Following completion of these assessments, all participants (except those who discontinued due to an AE or who have withdrawn consent) will immediately continue into Part 2 at Visit 25.

Note: In the event of tolerability issues at any time during the study, dosing may be decreased or temporarily stopped. If dosing is resumed during the Double-Blind Treatment Period at a dose level less than that achieved at Visit 9, attempts will be made every 4 to 8 weeks to re-establish the previously achieved dose level from Visit 9, if medically appropriate. If study drug is interrupted for longer than 8 weeks, then study drug treatment will be permanently discontinued.

Part 2:

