Lixivaptan Re-Titration Period (Visits 26 to 29): For all participants, titration of lixivaptan will occur over a 2 to 4-week re-titration period and will start at a dose of 50 mg BID beginning at the conclusion of Visit 25. The dose will be increased at weekly intervals until the dose level from the end of the Double-blind, Randomized Treatment Period in Part 1 is achieved. In order to maintain blinding of the treatment assignment from Part 1, the dose level assignment for Part 2 will continue to be managed by the IRT. The dose-titration schedule for this part of the study is described in [Table 2](#). In the event of tolerability issues,

dosing may be decreased. **Note:** during the Re-titration Period of Part 2, all participants are re-titrated with lixivaptan to the last actual dose level if they had received lixivaptan during the Double-blind, Randomized Treatment Period, or, if they had received placebo during the Double-blind, Randomized Treatment Period, to the last inferred dose level (the dose level equal to the active dose level had the participant been randomized to the active arm). Re-titration will be performed by the IRT, and the site, participant, and sponsor maintain a blinded status to the prior treatment assignment in Part 1. If no adjustment is made to the inferred dose during the Double-Blind, Randomized Treatment Period, the last inferred dose for a participant randomized to placebo will be equal to the maximal tolerated lixivaptan dose established during the Titration Period in Part 1.

Maintenance Treatment Period (Visits 30 to 42): Following completion of the Lixivaptan Re-titration Period, participants will continue to receive lixivaptan in the Maintenance Treatment Period for 52 weeks at the same dose achieved at the end of the Re-titration Period in Part 2. If the participant's dose was decreased during the Lixivaptan Re-Titration Period, attempts will be made every 4 to 8 weeks to re-establish the previously achieved dose level (actual or inferred) at the end of the Double-blind, Randomized Treatment Period of Part 1. Visits will be performed every 4 weeks during this period. Assessments at each visit are detailed in the [Schedule of Procedures – Part 2](#).

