- **Per-protocol Efficacy Analysis Set (PPAS):** The PPAS includes all participants in the PEAS who do not have any protocol deviations that are deemed to potentially impact efficacy.

Assignment of participants to populations will be confirmed at a blinded data review meeting to be held before the study database is locked for Part 1.

Part 2:

- **Part 2 Safety Set (P2SS):** The Part 2 Safety Set includes all participants who receive at least one dose of lixivaptan in Part 2.
- **Part 2 Efficacy Analysis Set (P2EAS):** The Part 2 Efficacy Analysis Set includes all participants in the Part 2 Safety Set who have at least one assessment of off-treatment eGFR in Part 2.

Parts 1 & 2 (Combined):

• Lixivaptan Treated Safety Set (LTSS): The Lixivaptan Treated Safety Set is defined as all participants who received at least one dose of lixivaptan treatment after randomization during the entire study. This analysis population will be used to summarize safety data during the study for all randomized, lixivaptan-treated participants.

6. General Issues for Statistical Analysis

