6.1.2. Treatment Group and Cohort

For Part 1 summaries after randomization, the analysis results will be presented by two treatment groups: lixivaptan and Placebo.

Since all participants in Part 2 are treated with lixivaptan, the summaries for Part 2 will be

presented in the following treatment cohorts and overall (treatment cohorts combined):

- Part1/Part2 Placebo/Lixivaptan: all participants in Part 2 who were randomized into Placebo treatment group in Part 1
- Part1/Part2 Lixivaptan/Lixivaptan: all participants in Part 2 who were randomized into lixivaptan treatment group in Part 1

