7.4. Exposure and Compliance

Exposure and compliance will be presented for Randomized Safety Set during the Double-Blind, Randomized Treatment Period (Part 1) and P2SS during the Maintenance Treatment Period (Part 2).

The duration of exposure will be presented in days and calculated as the date of last dose in treatment period minus the date of first dose in treatment period, plus one. Duration of exposure

and total dose taken (mg) will be summarized using descriptive statistics by treatment group (treatment cohort in Part 2).

Compliance to study drug is calculated by dividing the total capsules taken by the total capsules the participants were scheduled to take during the treatment period:

Treatment Compliance (%) = $\frac{total Capsules Taken}{Total Capsules Scheduled} \ge 100$

Dosing compliance will be summarized using descriptive statistics by treatment group (treatment cohort in Part 2). The number and percentages of participants who are < 80% compliant and $\ge 80\%$ compliant overall in the study will be summarized.

8. Efficacy Analysis

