8.12. Additional Analyses (Part 2)

Additional exploratory analyses may be conducted to address any issues caused by potentially different treatment/exposure patterns between Part 1 and Part 2 for the participants in the P2EAS.

9. Safety and Tolerability Analysis

Safety will be evaluated from reported AEs, changes in clinical laboratory values, changes in

vital signs, and electrocardiogram (ECG results).

A Safety Analyses will be performed for the following:

- Single-Blind Placebo Run-in Period for the Placebo Run-in Safety Set (Part 1)
- Lixivaptan Titration Period for the Lixivaptan Treated Safety Set (Part 1)
- Double-blind, Randomized Treatment and Follow-up I Periods for the Randomized Safety Set (Part 1)
- Maintenance Treatment and Follow-up II Periods for the P2SS (Part 2)
- Double-blind, Randomized Treatment and Follow-up I Periods and Maintenance Treatment and Follow-up II Periods for the LTSS (Part 1 and Part 2 combined)

The tolerability will be summarized by:

- Incidence of participants with the maximum dose level taken by the final tolerated dose level determined for the double-blind treatment period during Lixivaptan Titration Period
- Count and percentage of participants up-titrated, down-titrated, remaining unchanged, or discontinued by the dose levels by visit (or time after titration initiation) during Lixivaptan Titration Period
- Count and percentage of participants by dose level by Visit (or time after randomization) during the double-blind treatment period in Part 1 by treatment group
- Count and percentage of participants by dose level by Visit (or time after initiation of maintenance period) during the maintenance period in Part 2 by treatment group

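### SAP 9.6 tabulates crude percentages with an adverse event side by side for cohorts observed on lixivaptan for about 114–116 and 58–60 weeks, so the columns cannot be compared and the pooled figure has no defined risk period

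*SAP*

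**What the plan says.** SAP section 5 defines the Lixivaptan Treated Safety Set (LTSS) as "all participants who received at least one dose of lixivaptan treatment after randomization during the entire study". SAP 9.6 then summarises "safety information occurred post the first dose of lixivaptan treatment after randomization during the study based on the LTSS by treatment cohort and overall". The listed outputs are the incidence of special liver events, a Kaplan-Meier curve for those liver events, and treatment-emergent adverse event (TEAE) tables built as in SAP 9.2, which counts the number and percent of participants.

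The two cohorts start the clock at different times. The Placebo/Lixivaptan cohort is "all participants in Part 2 who were randomized into Placebo treatment group in Part 1" (SAP 6.1.2), so its first post-randomisation lixivaptan dose comes at the start of Part 2. The Lixivaptan/Lixivaptan clock starts at randomisation.

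SAP section 9 gives the LTSS periods as "Double-blind, Randomized Treatment and Follow-up I Periods and Maintenance Treatment and Follow-up II Periods for the LTSS (Part 1 and Part 2 combined"). That list leaves out re-titration, which the 9.6 wording would include.

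On exposure, SAP 7.4 says: "Exposure and compliance will be presented for Randomized Safety Set during the Double-Blind, Randomized Treatment Period (Part 1) and P2SS during the Maintenance Treatment Period". No exposure summary is planned for the combined LTSS. SAP 8.12 allows extra exploratory work on differing exposure patterns, but only for the Part 2 efficacy set.

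**The concern.** A crude percentage rises with the time a participant is watched. When one column covers about twice the time of the other, it will usually be higher even if lixivaptan carries the same risk in both cohorts. A reader could take the difference as harm building up with longer treatment, or as a difference between cohorts. The overall column mixes roughly one-year and two-year windows. SAP section 15 says the table was added to show overall safety for all lixivaptan-treated participants across the whole study, so it is the natural place to look up a lixivaptan adverse-event percentage.

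**Working it through.** **Inputs.** From Protocol 3.1.2: double-blind treatment ("matching placebo in a double-blind fashion for 52 weeks" for the comparator arm), 52 weeks; Follow-up I ("Three visits will occur over a 28-day, study drug-free period following the last dose of study drug"), 4 weeks; re-titration ("titration of lixivaptan will occur over a 2 to 4-week re-titration period"), 2–4 weeks; Follow-up II, 28 days, 4 weeks. From Protocol 6.7: maintenance, 52 weeks.

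**Reproducing the plan's durations.** Part 1 is 3+1+5+52+4 = 65 to 8+1+6+52+4 = 71 weeks. Part 2 is 2+52+4 = 58 to 4+52+4 = 60 weeks. Both match the protocol synopsis.

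**Windows under SAP 9.6.**

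| Re-titration | Lixivaptan/Lixivaptan | Placebo/Lixivaptan | Ratio |
|---|---|---|---|
| 2 weeks | 52+4+2+52+4 = 114 | 58 | 1.97 |
| 3 weeks | 115 | 59 | 1.95 |
| 4 weeks | 116 | 60 | 1.93 |
| Omitted (SAP section 9 list) | 112 | 56 | 2.00 |

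Counting only weeks on drug gives 106–108 against 54–56, a ratio of 1.93–1.96. Neither the re-titration question nor the drug-free follow-up changes the picture.

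**Effect on crude percentages (illustration).** Assume the same constant hazard in both cohorts, full follow-up and the midpoint windows of 115 and 59 weeks. If p is the Placebo/Lixivaptan incidence, the Lixivaptan/Lixivaptan incidence is 1 − (1 − p)^(115/59).

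| p | Lixivaptan/Lixivaptan | Ratio | Ratio with 10% Part 1 dropout |
|---|---|---|---|
| 4.4% | 8.4% | 1.91 | 1.77 |
| 20% | 35.3% | 1.76 | 1.64 |
| 30% | 50.1% | 1.67 | 1.56 |
| 50% | 74.1% | 1.48 | 1.39 |
| 70% | 90.4% | 1.29 | – |

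The last column assumes that 10% of the lixivaptan arm stops evenly over the 52 double-blind weeks and is then watched for 4 weeks. The 10% follows from the protocol's projection that 90% continue into Part 2; the even timing is my assumption. The 4.4% is only a convenient low value. It is the clinical tolvaptan figure in Protocol Table 5, not a 59-week lixivaptan risk.

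**Overall column.** With 2:1 randomisation and full follow-up, at p = 20% the pooled figure is (2 × 35.3 + 20)/3 = 30.2%. That is neither the 59-week risk (20%) nor the 115-week risk (35.3%).

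**After adjustment.** With equal constant hazards, a person-time rate gives a cohort ratio of 1.0. So does a Kaplan-Meier estimate read at a common time.

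**The case against.** The strongest reply is that comparable windows already exist elsewhere. SAP section 9 plans separate safety analyses for double-blind treatment plus Follow-up I and for maintenance plus Follow-up II, each 52+4 = 56 weeks, and the Part 2 tables are by cohort. SAP 9.6 is descriptive, with no test between cohorts, and the cohort names signal one versus two parts on drug. This stands as mitigation: a careful reader could find similar windows. It does not correct the pooled table, which prints the unequal columns together and an overall figure with no time base. SAP 7.4 gives no LTSS exposure to set beside them.

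A reader might infer that liver safety is misreported. The documents do not support that. SAP 9.6 plans a Kaplan-Meier curve for the special liver events, including ALT above 3 × ULN, and this allows for unequal follow-up. Only the crude liver-incidence line is affected, although no time point for reading the curve is given.

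A reader might also infer a fixed excess of 1.6 to 1.9 for harms in general. That band needs a constant hazard and a Placebo/Lixivaptan incidence of about 5–37%. Very common rows, possibly including any TEAE, would fall below it. Constant hazard is doubtful for common effects: Protocol 1.9 describes them as exaggerated pharmacology, such as increased urine output and thirst. If such events cluster soon after starting drug, the ratio moves towards 1.

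**Conclusion.** The point holds for the TEAE tables in SAP 9.6 and for the single crude liver line. The design makes the windows differ about two-fold, and nothing planned for the LTSS percentages allows for it. That rests on stated durations alone.

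The size of the distortion is conditional. With equal constant hazard and full follow-up the ratio is about 1.9 to 1.7 for incidences of 4.4% to 30%. It is smaller for commoner events and with Part 1 dropout, and could be near 1 for early-onset events. The documents give no lixivaptan event rates or onset patterns that would settle it.

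It would also go too far to infer that a reported result is wrong. SAP section 12 records that only 5 participants were randomised, all ended early in Part 1, and no statistical analyses will be performed. The point concerns the plan as written. It is an inexpensive improvement and does not threaten the trial's conclusions.

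**What to change.** 1. In SAP 9.6, add exposure-adjusted incidence for the overall TEAE summary and the preferred-term tables: participants with an event per 100 person-years, with time at risk from the first post-randomisation lixivaptan dose to first event or end of observation.
2. Make any side-by-side cohort comparison over the first 52 weeks after that dose, and read the liver Kaplan-Meier estimates at the same time. A longer window would bring the drug-free Follow-up I into the Lixivaptan/Lixivaptan column.
3. Add LTSS exposure, by cohort and overall, to SAP 7.4.
4. State whether re-titration belongs to the LTSS window, since SAP section 9 and SAP 9.6 differ.
5. Footnote that crude cumulative percentages are not to be compared across cohorts.

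**Cost.** SAP wording, extra table columns, and time at risk derived separately for each reported event row. Dosing and event dates are already collected, and time to first event is already planned for liver events in SAP 9.3.1. Person-time rates assume a roughly constant hazard; the 52-week table does not. Even that table is not a randomised comparison: Placebo/Lixivaptan contains only people who continued into Part 2, and its first 52 weeks begin with 2–4 weeks of re-titration. No visit, dose or procedure changes.
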